4.3.4.1.1 INDEPENDENT PHOTOGRAPHIC ASSESSMENTS

Three experienced, blinded photographic reviewers will perform a qualitative analysis/review of the pre-treatment and post-treatment sets of images of each subject in a blinded and randomized order. Each

Apyx Medical Corporation

Protocol Number: APX-22-04-GR

Effective Date: October 2, 2023

Revision No: 04

Title: A Post-Market Study in Greece of a Minimally Invasive Lower Eyelid Treatment Utilizing the Renuvion System Clinical Trial Protocol

blinded reviewer will choose which image is the post-treatment image. Success will be correct post-treatment image selection by at least 2 out of 3 reviewers. The percentage of subjects with a correct post-treatment image selection will be calculated.

Assessment of each subject's baseline and follow-up images viewed simultaneously will be performed by the Independent Photographic Reviewers (IPR) who will be blinded to the study subject's visit (baseline and follow-up visit). Each IPR will view each subject's randomized pre-treatment and post-treatment images and assess which set of images represent the subject's post-treatment images. Each photograph will have a unique identification number, but the sets of images will not be arranged in any specific order (i.e., randomized order). The Sponsor will prepare and administer the IPR.

4.3.4.1.2 INDEPENDENT PHOTOGRAPHIC REVIEW EVALUATION PROCESS

Each blinded assessor will be provided with identical photos to be assessed. The pre-treatment and post-treatment photos will be consistent in lighting, subject positioning, and focus. Each photo's visit interval, i.e., pre-treatment and post-treatment, will NOT be marked. The images placement (right or left) will be randomly ordered for pre-treatment and post-treatment images. Images for each subject will be grouped together into one set with all pre-treatment and post-treatment images in the same location (right/left) for the subject set.

Each blinded assessor will conduct their assessment independently with no input from another blinded assessor.

Each blinded assessor compares the Left and Right photo for change that may be striking (substantial and immediately noticeable), readily apparent but modest in nature, or slight and subtle in nature that may require close examination. Assessors should look through each view and assess change. Enough time should be allowed to do this for each subject, so the assessments are not rushed.

The assessor chooses which photo they believe to be the post-treatment photo (i.e., Left photo or Right photo) once all images in the subject set have been reviewed.

Post-Analysis Coding of Masked Assessment:

- If the assessor incorrectly chooses the post-treatment photo, this will be coded as an "Incorrect post-treatment selection".
- If the assessor correctly chooses the post-treatment photo, this will be coded as a "Correct post-treatment selection".
- Success will be determined by correct identification of post-treatment photographs by at least two out of three blinded, independent reviewers.

4.3.4.1.3 INDEPENDENT PHOTOGRAPHIC REVIEW TRAINING PROCESS

IPR assessors will participate in a training session prior to completing the IPR. The purpose of the training is to provide guidance to the IPR assessors on the methods for reviewing the study images. Instructions will include that each blinded assessor should pay close attention to changes in:

- Lower Eyelid laxity
- Lower Eyelid fine lines and wrinkles
- Overall appearance of the treatment area

4.3.4.2 SNAP-BACK TEST GRADE

Analysis of change from baseline to D30, D90, and D180 in the Snap-back Test Grade¹⁴. This test provides relative lower lid laxity. In normal lids, the skin snaps-back to the original position immediately; the longer it takes, the more laxity is present.

To perform the snap-back test, pull the lower lid away and down from globe for several seconds and wait to see how long it returns to the original position without the subject blinking.

Grade 0 – IV (0 = normal, IV = severe laxity):

- Grade 0 – Normal lid that returns to position immediately on release.
- Grade I – Approximately 2-3 seconds to return to original position.
- Grade II – 4-5 seconds to return to original position.
- Grade III - >5 seconds but does return to original position with blinking.
- Grade IV – Never returns to original position and continues to hang down in frank ectropion after the snap-back test.

FIGURE 3: SNAP-BACK TEST

4.3.4.3 MEDIAL CANTHAL LAXITY TEST GRADE

Analysis of change from baseline to D30, D90, and D180 in the Medial Canthal Laxity Test¹⁴. This test provides medial canthal laxity by means of measuring displacement. The greater the distance, the more the laxity.

To perform the medial canthal laxity test, pull the lower lid laterally away from the medial canthus and measure displacement of medial punctum.

Grade 0 – IV (0 = normal, IV = severe laxity):

- Grade 0 – <2mm displacement.
- Grade I – Approximately 2mm displacement.
- Grade II – Approximately 3mm displacement.
- Grade III - >3mm displacement.
- Grade IV – Does not return to baseline after release and blinking

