4.3.3 ADDITIONAL OUTCOME MEASURES

1. Improvement in the lower eyelid area as determined by a masked, qualitative assessment of photographs at 90-days post-treatment compared to baseline.
2. Analysis of change from baseline to D30, D90, & D180 in Snap-back Test Grade (Bashour¹⁴).
3. Analysis of change from baseline to D30, D90, & D180 in Medial Canthal Laxity Test Grade (Bashour¹⁴).
4. Analysis of change from baseline to D30, D90, & D180 in Lateral Canthal Laxity Test Grace (Bashour¹⁴).
5. The investigator will complete a GAIS¹³ assessing overall aesthetic improvement in the treatment area at day 30, 90, and 180 post-treatment.
6. The subject will complete a GAIS¹³ assessing overall aesthetic improvement in the treatment area at day 30, 90, and 180 post-treatment.
7. The subject will complete a Patient Satisfaction Questionnaire (PSQ) at the 180-day follow-up visit.
8. During study treatment, the subject's pain levels will be monitored using the 11-point Numeric Rating Scale (NRS)²⁰. The average pain score for the entire region treated will be recorded. Pain scores will be recorded at all follow-up visits.

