4.3.4.4 LATERAL CANTHAL LAXITY TEST GRADE

Analysis of change from baseline to D30, D90, and D180 in the Medial Canthal Laxity Test¹⁴. This test provides lateral canthal laxity by means of measuring displacement. The greater the distance, the more the laxity.

To perform the lateral canthal laxity test, pull the lower lid medially away from the lateral canthus and measure displacement of lateral canthal corner.

Apyx Medical Corporation

Protocol Number: APX-22-04-GR

Effective Date: October 2, 2023

Revision No: 04

Title: A Post-Market Study in Greece of a Minimally Invasive Lower Eyelid Treatment Utilizing the Renuvion System Clinical Trial Protocol

Grade 0 – IV (0 = normal, IV = severe laxity):

- Grade 0 – <2mm displacement.
- Grade I – 2-4mm displacement.
- Grade II – 4-6mm displacement.
- Grade III - >6mm displacement.
- Grade IV – Does not return to baseline after release and blinking

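### The two canthal laxity tests measure a displacement in mm, but only the grade is named as collected and analysed, so small changes and changes within Grade 0 or Grade III read as zero

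*Combined protocol and SAP*

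**What the plan says.** The medial test (protocol 4.3.4.3) instructs the examiner to "pull the lower lid laterally away from the medial canthus and measure displacement of medial punctum". The lateral test (4.3.4.4) instructs the examiner to "pull the lower lid medially away from the lateral canthus and measure displacement of lateral canthal corner". Both sections say that a greater distance means more laxity.

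Each distance is then turned into a grade:

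- **Medial:** Grade 0 is below 2 mm and Grade I is about 2 mm. The next two are "Grade II – Approximately 3mm displacement" and "Grade III - >3mm displacement".
- **Lateral:** Grade 0 is below 2 mm. Next come "Grade I – 2-4mm displacement", then 4-6 mm for Grade II, then "Grade III - >6mm displacement".
- **Both:** Grade IV is failure to return after release and blinking. It is not a distance.

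The outcome in 4.3.3 is "Analysis of change from baseline to D30, D90, & D180 in Medial Canthal Laxity Test Grade", with the same form for the lateral test. Section 14.1 lists laxity grades among the data collected. No section says that the mm value is kept or summarised, and none forbids it. Section 10.1 plans descriptive statistics only. Section 10.2 allows up to 16 treated subjects. Entry requires only a complaint of laxity or lines (5.2), with no minimum grade.

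**The concern.** The examiner has to obtain a distance in order to assign the grade, yet the plan names only the grade. The distance cannot be recovered from the grade afterwards.

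Three kinds of change are hidden:

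- a change smaller than the band in which the subject sits;
- any change, better or worse, that stays inside the open-ended Grade III;
- any improvement in a subject who starts in Grade 0, which the entry criteria allow.

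The primary endpoint asks only which photograph is post-treatment, so it gives no size of change. The canthal tests are the outcomes that could give laxity change in mm. With so few subjects, a mean grade change near zero would be hard to tell apart from no effect.

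**Working it through.** The protocol states no effect size, SD, test or sample-size derivation, so there is no figure of its own to reproduce. All effects, baselines and errors below are assumptions.

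**Step 1. Share of changes that read as zero, by arithmetic.**

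Inside closed bands of width w, with baselines spread evenly, a reduction d leaves the grade unchanged in a share max(0, 1 - d/w).

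- Lateral Grades I-II, w = 2 mm: d = 0.5 gives 1 - 0.5/2 = 75%; d = 1 gives 50%; d = 2 gives 0%.
- Medial Grades I-II, w = 0.5 mm (literal reading, cut at 2.5 mm): d = 0.25 gives 50%; d = 0.5 gives 0%.
- Medial Grades I-II, w = 1 mm (readings rounded to the nearest mm): d = 0.5 gives 50%; d = 1 gives 0%.

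Inside Grade III, with baselines spread evenly from the cut c up to an assumed maximum U, the share is 1 - d/(U - c).

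- Lateral, 6 to 10 mm: d = 0.5 gives 1 - 0.5/4 = 88%; d = 1 gives 75%; d = 2 gives 50%.
- Medial, 3 to 6 mm: d = 0.25 gives 1 - 0.25/3 = 92%; d = 1 gives 67%; d = 2 gives 33%.

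For lateral baselines spread over 0.5-8 mm, simulation gives 80%, 60% and 20% for d = 0.5, 1 and 2 mm. Across these settings the share runs from 0% to about 92%.

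**Step 2. Index of lost information.**

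Assume N = 16, one value per subject, a true reduction of 0.5 mm in everyone, and independent measurement error of SD 0.5 mm at each visit. Baseline SD is 1.5 mm (lateral) or 1.0 mm (medial), and the comparison is a paired t-test at two-sided 5%.

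On mm, the SD of the change is √2 × 0.5 = 0.71 mm. The noncentrality is 0.5 / (0.71/√16) = 2.83, which on 15 df gives power of about 75%.

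On grade, the same readings (to 0.1 mm) are cut into bands. Lateral cuts are 2, 4 and 6 mm, with 4 mm placed in Grade I because the protocol's bands share that value. Medial cuts are 1.75, 2.5 and 3.25 mm, an assumed reading of the approximate grades. Simulation gives:

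| Test and baseline mean | Power on mm | Power on grade |
|---|---|---|
| Lateral, 3-5 mm | about 75% | 35-39% |
| Lateral, 7 mm | about 75% | about 20% |
| Medial, 2.5 mm | about 75% | about 54% |
| Medial, 3.5 mm | about 75% | about 45% |
| Medial, 4.5 mm | about 75% | about 16% |

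**Step 3. Sensitivity.**

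- Literal medial cuts (2, 2.5, 3 mm): grade power is roughly 50%, 41% and 9% at the three baselines, so the assumed cuts do not create the gap.
- Whole-mm readings, lateral: about 60-64% on mm against 25-35% on grade.
- Whole-mm readings, medial baseline mean 2.5 mm: about 61% against 53%, so the gap nearly closes.
- A 1.0 mm reduction, same error SD: the gap is 2-3 points for medial baseline means of 2.5 and 3.5 mm, and about 9-27 points in the other settings.

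**The case against.** A reader might infer that most real changes in laxity will read as zero. The documents do not support that. They give neither a baseline distribution nor an expected change, and a 2 mm lateral change within Grades I-II is never missed. The largest losses in the working come from a change as small as the assumed measurement error, or from subjects who start in Grade III. Nothing in the protocol suggests that many will.

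A reader might also extend the point to snap-back. There the examiner must "wait to see how long it returns to the original position without the subject blinking", but Grade III is described by return with blinking and Grade IV by no return. Seconds are therefore not one clean continuous scale, and no loss has been quantified for that test.

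Nor are these the only non-photographic views of laxity. The GAIS includes a live assessment, and the satisfaction questionnaire, completed with a mirror as well as photographs, asks about sagging skin.

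Four further objections carry weight. The plan runs no test, so no planned decision turns on power. The outcomes are secondary. The grades come from a cited scale and should stay. The CRF is not in the documents, so mm may already be written down.

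What survives is narrower: the named outcome and the named data item are the grade, a measured distance lies behind it, and no reason is given for leaving the distance out.

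**Conclusion.** The point holds for the two canthal tests. By the protocol's own cuts, small changes and changes within Grade 0 or Grade III read as zero, and no section commits to keeping the measurement that would show them. How much is lost is unknown: 0% to about 92% of changes, depending on baseline and effect. The power figures (about 75% on mm against 20-39% lateral and 16-54% medial) rest on a 0.5 mm change, error SD 0.5 mm and 0.1 mm readings. They only illustrate lost information in a descriptive plan. The lateral gap for that change survives whole-mm reading. The medial gap depends more on baseline and reading resolution, and almost disappears in some settings. This is a cheap gain in precision for two secondary outcomes; it does not threaten the primary endpoint.

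**What to change.** - **Laxity CRF:** record displacement in mm for each lid (medial and lateral, right and left) at baseline, D30, D90 and D180, at a stated reading resolution.
- **Sections 4.3.3 and 10.1:** summarise change from baseline in mm (n, mean, SD, median, range, 95% interval) beside the change in grade. Use the mean of the two lids per subject, and report Grade IV as a count.
- **Snap-back:** keep the grade as the outcome. Return time may also be recorded, summarised by median and range only, with return on blinking and no return counted separately. Capped times should not enter a mean.

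The cost is four numeric fields per laxity assessment for the canthal tests (two tests × two lids) and a sentence or two in the protocol. No visit or test is added. Subjects assessed before the change will have grade only, so the mm summary must state its own n.

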4.3.4.4 LATERAL CANTHAL LAXITY TEST GRADE

Analysis of change from baseline to D30, D90, and D180 in the Medial Canthal Laxity Test¹⁴. This test provides lateral canthal laxity by means of measuring displacement. The greater the distance, the more the laxity.

To perform the lateral canthal laxity test, pull the lower lid medially away from the lateral canthus and measure displacement of lateral canthal corner.

Apyx Medical Corporation

Protocol Number: APX-22-04-GR

Effective Date: October 2, 2023

Revision No: 04

Title: A Post-Market Study in Greece of a Minimally Invasive Lower Eyelid Treatment Utilizing the Renuvion System Clinical Trial Protocol

Grade 0 – IV (0 = normal, IV = severe laxity):

- Grade 0 – <2mm displacement.
- Grade I – 2-4mm displacement.
- Grade II – 4-6mm displacement.
- Grade III - >6mm displacement.
- Grade IV – Does not return to baseline after release and blinking

4.3.4.5 GLOBAL AESTHETIC IMPROVEMENT SCALE (GAIS)

The Global Aesthetic Improvement Scale (GAIS) is a scale that rates global aesthetic improvement from the pretreatment appearance¹³. In this study both live observation and photo review are utilized by the physician or a qualified, delegated clinician and subject in order to assign a score. The PGAIS (Physician Global Aesthetic Improvement Scale) must be performed by the principal investigator. Both the PGAIS and SGAIS (Subject Global Aesthetic Improvement Scale) should be completed in two steps:

- Based on a live assessment of the subject while referring to the subject's pre-treatment photographs (subjects should be given a hand mirror for assessment); and
- Based on a comparison of the subject's pre-treatment photographs to the current post-treatment photographs.

The Investigator will grade the overall improvement of treatment area as indicated in **Table 3** by comparing the subject's appearance at follow-up visits against a photograph taken prior to procedure. Likewise, the subject will also rate their improvement compared to pre-treatment as shown in **Table 4**. The modified GAIS results will be collected at the 30-day, 90-day, and 180-day follow-up visits.

TABLE 3: MODIFIED GLOBAL AESTHETIC IMPROVEMENT SCALE EVALUATION - INVESTIGATOR

Rating	Description
Very much improved	Optimal cosmetic result from this procedure in this subject
Much improved	Marked improvement in appearance from the initial condition, but not completely optimal for this subject
Improved	Obvious improvement in appearance from the initial condition
No change	The appearance is essentially the same as the original condition
Worse	The appearance is worse than the original condition
Much worse	The appearance is much worse than the original condition
Very much worse	The appearance is very much worse than the original condition

TABLE 4: MODIFIED GLOBAL AESTHETIC IMPROVEMENT SCALE EVALUATION - SUBJECT

[figure not shown]
Rating	
Very much improved	
Much improved	
Improved	
No change	
Worse	
Much worse	
Very much worse	

4.3.4.6 SUBJECT SATISFACTION SURVEY

The study subjects will be asked to complete a Subject Satisfaction Survey (**Appendix A**) at the 180-day follow-up visit. The subject should complete this assessment while referring to baseline photos, current photos, and a hand mirror.

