APPENDIX A: PATIENT SATISFACTION QUESTIONNAIRE

Please have the subject complete this assessment while referring to their image in the mirror and current post-treatment photos compared to baseline photos. Provide the subject with a mirror.

Using a mirror and reviewing your post-treatment photos, compare how your treatment area currently looks compared to your pre-treatment photos.

1. Do you notice any improvement in how your lower eyelid area?
 YES → Improvement in wrinkles
 Less sagging skin
 Smoother skin texture
 Other: _____
 NO

2. How would you characterize your satisfaction with the treatment?
 Very Satisfied
 Satisfied
 Slightly Satisfied
 Neither Satisfied or Dissatisfied
 Slightly Dissatisfied
 Dissatisfied
 Very Dissatisfied

3. Would you recommend this treatment to your friends and family members (check one)?
 YES NO

Thank you for completing this questionnaire.

Subject Initials: _____

Date: _____ (DD/MON/YYYY)

Apyx Medical Corporation

Protocol Number: APX-22-04-GR

Effective Date: October 2, 2023

Revision No: 04

Title: A Post-Market Study in Greece of a Minimally Invasive Lower Eyelid Treatment Utilizing the Renuvion System Clinical Trial Protocol

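### Item 1 of the D180 satisfaction form can record only improvement, so a subject has no way to report that wrinkles, sagging or skin texture got worse

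*Combined protocol and SAP*

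**What the plan says.** Section 4.3.3 makes the form additional outcome measure 7: "The subject will complete a Patient Satisfaction Questionnaire (PSQ) at the 180-day follow-up visit". Section 4.3.4.6 states "The study subjects will be asked to complete a Subject Satisfaction Survey", points to Appendix A as the instrument and sets the conditions: "The subject should complete this assessment while referring to baseline photos, current photos, and a hand mirror".

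Appendix A has three items.

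- **Item 1** asks "Do you notice any improvement in how your lower eyelid area". YES opens a short list of improvements (wrinkles, "Less sagging skin", texture, and a free-text Other). NO has no follow-up.
- **Item 2** asks "How would you characterize your satisfaction with the treatment" on seven levels: three positive, one neutral and three negative, ending at "Very Dissatisfied".
- **Item 3** is a YES/NO question on recommending the treatment.

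Section 4.3.4.5 (Table 4) also has the subject complete a seven-level GAIS at Days 30, 90 and 180, with three levels for worsening. Section 10.1 plans descriptive statistics only, with categorical variables given as counts and percentages in each category.

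**The concern.** The study is single-arm, and subjects know they were treated. In that setting a subject-reported item should be able to show change in either direction. Item 1 cannot. Its Other field sits under YES, so even free text is reserved for improvements. A subject who sees more sagging, more lines or a visible scar has nowhere on item 1 to say so.

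A YES percentage is the natural summary of this item under Section 10.1. A reader could take the remainder as subjects with no change, when some may be worse. A reader could also take each YES as a subject who is better on balance, when some may have a feature that deteriorated. Section 2.2.1 itself lists pigmentation change, unsatisfactory scarring, asymmetry and an unacceptable cosmetic result as risks, so visible worsening is a foreseen outcome.

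**Working it through.** The plan states no expected survey percentage, power or threshold, so there is no figure to reproduce. The check is on what item 1 can and cannot distinguish.

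**Inputs.** n = 16, the maximum number treated (Section 10.2). Response options are from Appendix A, and GAIS levels from Section 4.3.4.5. All splits below are assumptions, because the documents give none.

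**Step 1: how true states map to item 1.** Let b = subjects with improvement only, m = mixed (at least one feature better and one worse), u = unchanged, w = worse only, with b + m + u + w = n.

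| State | Item 1 answer | Worsening recorded by item 1 |
|---|---|---|
| Better only (b) | YES | none to record |
| Mixed (m) | YES | no |
| Unchanged (u) | NO | none to record |
| Worse only (w) | NO | no |

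So YES = b + m and NO = u + w. The number with at least one worse feature is m + w, and item 1 shows none of them.

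**Step 2: does pooling raise the YES percentage?** YES/n = (n − u − w)/n. Moving subjects between u and w leaves u + w, and hence YES/n, unchanged. Every split at n = 16 was enumerated and gave a difference of 0 points. Examples: 8/16 = 50.0%, 10/16 = 62.5% and 12/16 = 75.0%, each the same whether or not NO is split.

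**Step 3: what is hidden.** Assume 8 YES, 5 unchanged and 3 worse. Item 1 reports 8/16 = 50% YES and 8/16 = 50% NO. The 3 worse subjects (3/16 = 18.75%) cannot be seen. If 0 to 3 of the 8 YES subjects are mixed, those with a worse feature number 3 to 6, that is 3/16 = 18.75% to 6/16 = 37.5%. Item 1 shows 0 in every case.

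**Step 4: leading wording, a separate mechanism.** If k unchanged or worse subjects answered YES because of how the question is put, the YES percentage would rise by k/16, or 6.25 points each. From an assumed 10/16 = 62.5%, k = 1, 2, 3 gives 68.75%, 75.0% and 81.25%. The documents contain nothing from which to choose k, and k = 0 is possible.

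**Step 5: do other instruments fill the gap?**

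- The subject GAIS separates worse from unchanged overall. It is one global rating, so it does not say which feature worsened, or show a worse feature within an overall improvement.
- Item 2 measures satisfaction, not the appearance of each feature.
- The laxity tests (Sections 4.3.4.2 to 4.3.4.4) grade lid return and displacement, and can show deterioration. Section 14.1 lists laxity grades among what subjects complete, but the tests are hands-on lid manoeuvres. They do not rate visible wrinkles or texture.
- The masked photograph review (Section 4.3.4.1.2) records which image was chosen as post-treatment, not the direction of change.
- Adverse event interviews can pick up scarring or asymmetry, but they are not a structured rating by feature.

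**The case against.** The strongest reply is that worsening is well covered elsewhere. The subject and investigator GAIS both have three worse levels at Days 30, 90 and 180. The laxity grades can move either way, and adverse events are sought at every follow-up visit. Item 2 is balanced and item 3 accepts a NO. Item 1 is one question within the seventh of eight additional outcomes in a descriptive study, and no section names its YES percentage as an endpoint or sets a threshold for it. All of that stands. It confines the gap to subject-rated worsening by feature, and it rules out any effect on the primary endpoint or the safety analysis.

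A reader might go further and infer three things that the documents do not support.

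- **That the whole survey asks only about improvement.** Items 2 and 3 show otherwise.
- **That counting worse subjects as NO inflates the YES percentage.** Both groups stay in the denominator as non-YES, so the effect is exactly 0.
- **That the reported figure is biased in the device's favour as a matter of fact.** One-sided wording put to unmasked subjects makes this plausible, but its size, and whether it occurs at all, cannot be established from the documents.

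Mixed change is different. Such a subject answers YES correctly, because the question asks about any improvement. The YES percentage is then a valid answer to a narrow question, but not a count of subjects who are better on balance.

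**Conclusion.** The point holds for item 1 of Appendix A and no further. The item cannot record worsening of wrinkles, sagging or texture, its NO merges unchanged with worse, and mixed change counts as YES. Each subject who falls into one of these cells is 6.25 points of 16, or more if fewer than 16 answer at Day 180. How many there will be is unknown, and the splits shown are illustrations only. Overall worsening remains visible through the D180 subject GAIS. Importance is modest. The change is worth making because it is cheap and turns a one-directional measure into one that can show either result.

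**What to change.** Reword Appendix A item 1 so that the subject compares the lower eyelid area with the pre-treatment photographs and rates each listed feature (wrinkles, sagging skin, skin texture, other) as better, about the same or worse. This also repairs the item's incomplete sentence. Keep items 2 and 3 as they are.

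Report the counts in all three categories for each feature, and present them beside the D180 subject GAIS distribution so that feature-level and overall ratings can be read together.

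The cost is a revised one-page form and IRB review, which Section 13.2 requires for participant materials. No visit, procedure or sample size changes. Any answers already given on the existing form must be reported separately, which divides a small sample. If the form cannot be changed, reporting item 1 beside the D180 subject GAIS would show overall worsening, but not which feature worsened.
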